5.2.2.4. Reverse Cumulative Distribution Curves

Empirical reverse cumulative distribution curves (RCDCs) will plot the proportion of subjects with values equal to or exceeding a specified assay value versus the indicated assay value, for all observed assay values. Data points will be joined by a step function with the data point on the left side of the step.

5.2.2.5. Nonparametric Comparison

As only a subset of subjects will be tested for cellular assays, small sample sizes are expected for each group. Therefore, nonparametric comparison between each RSVpreF dose/formulation group and the placebo group on each of the assay values at each applicable time point will be performed and exact p-values based on the 2-sample Wilcoxon test will be provided for these comparisons.

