2.2. Study Design

This is a Phase 1/2, multicenter, randomized, placebo-controlled, observer-blind, dose- and formulation-finding study.

The study will evaluate the safety, tolerability, and immunogenicity of up to 7 different RSV vaccine candidates with bivalent formulations (RSV A and RSV B) at 3 dose levels of 60 µg of the prefusion RSV F antigens CCI [REDACTED] 120 µg CCI [REDACTED] and 240 µg CCI [REDACTED] formulated with aluminum hydroxide (Al[OH]₃) or CpG/Al(OH)₃, or a 240-µg RSV vaccine CCI [REDACTED] alone, when administered concomitantly with SIIV, or 240 µg formulated with CpG/Al(OH)₃ on a Month-0 and Month-2 schedule without SIIV.

The study is organized in the following cohorts:

1. The Primary Study Cohort - Stage 1 will evaluate 7 RSV vaccine doses/formulations given concomitantly with SIIV at Month 0.
2. The Primary Study Cohort - Stage 2 will evaluate revaccination of the Stage 1 subjects with the RSV vaccine and concomitant SIIV, administered at Month 12.
3. The RSV Vaccine Month-0, Month-2 Cohort will evaluate a 240-µg dose of the RSV vaccine with CpG/Al(OH)₃ given at Months 0 and 2. No concomitant SIIV will be given.

Male and female subjects 65 to 85 years of age will be enrolled. Subjects will be randomized equally across all dose groups in the primary cohorts. The RSV Vaccine Month-0, Month-2 Cohort will be randomized 1:1 to receive RSV vaccine or placebo.

Primary Study Cohort - Stage 1. Enrollment in the Primary Study Cohort - Stage 1 commenced in April 2019 and completed in June 2019. Approximately 250 subjects 65 to 85 years of age were equally randomized at Visit 1 to receive one of the 7 RSV vaccine doses/formulations or placebo (a total of 8 parallel groups), concomitantly with SIIV.

Primary Study Cohort - Stage 2. Prior to completion of Stage 1, subjects may be invited to participate in Stage 2. Safety and immunogenicity data obtained from the C3671001 and C3671002 studies will be used to determine whether Stage 2 will proceed and, if so, whether all or some of the RSV formulations will be evaluated.

Two protocol administrative change letters (PACLs) were distributed to the sites regarding initiation of Stage 2 vaccination. The first PACL, dated in January 2020, was to instruct the sites that all subjects would be revaccinated in Stage 2. The second PACL, dated in March 2020, was to instruct sites to postpone the initiation of Stage 2 until further notice because of the coronavirus disease 2019 (COVID-19) pandemic.

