5. GENERAL METHODOLOGY AND CONVENTIONS

5.1. Hypotheses and Decision Rules

5.1.1. Statistical Hypotheses

This Phase 1/2 study is designed to describe the safety, tolerability, and immunogenicity of the RSV vaccine alone or formulated with Al(OH)₃ or CpG/Al(OH)₃, when administered concomitantly with SIIV, and a 240-μg dose of the RSV vaccine with CpG/Al(OH)₃, but without SIIV. No formal statistical hypothesis testing will be performed. An estimation approach will be used to assess the safety and immunogenicity objectives.

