5.1.2. Statistical Decision Rules

Statistical decision rules will not be utilized in this study. All analyses are considered descriptive in nature.

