6.3. Other Endpoint(s)

6.3.1. Plasmablast Frequencies and T-Cell Phenotype and Functional Analysis

For each cohort, descriptive statistics (median, n, and range [minimum-maximum]) will be summarized for each relevant assay at each applicable time point, among subjects included in the evaluable immunogenicity population.

Additionally, the exact p-value from the Wilcoxon 2-sample test will be used to compare each RSVpreF dose/formulation group and placebo group.

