7.2. Interim Analyses and Summaries

- **Primary Study Cohort - Stage 1**

An analysis will be conducted when 1-month post-Vaccination 1 immunogenicity data from all subjects in the Primary Study Cohort - Stage 1 are available. All available safety, tolerability, and immunogenicity data from subjects will be included in the analysis.

- **Primary Study Cohort - Stage 2**

An analysis will be conducted when 1-month post-Vaccination 2 immunogenicity data from all subjects in the Primary Study Cohort - Stage 2 are available. All available safety, tolerability, and immunogenicity data will be included in the analysis.

- **RSV Vaccine Month-0, Month-2 Cohort**

An analysis will be conducted when 1-month post-Vaccination 2 immunogenicity data from all subjects in this cohort are available. All available safety, tolerability, and immunogenicity data will be included in the analysis.

Assays may come in batches; therefore, some interim analyses may be performed in batches. One interim analysis may span multiple reporting events. The results of these analyses will be used to select the most appropriate dose(s), formulation(s), and dosing schedule of the RSV vaccine for use in further studies in older adults.

Additional analyses may be conducted before the final analysis to support other internal program-level decisions as needed.

Safety data will be summarized on an ongoing basis.

No multiplicity adjustments will be applied for these analyses.

The final analysis will be performed after all the subjects complete the study and when all of the data are available.

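### The SAP promises estimation, but the cellular assays are compared with placebo only by unadjusted exact Wilcoxon p-values, with no between-group estimate or confidence interval

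*SAP*

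**What the plan says.** SAP 5.1.1 sets the framework: "No formal statistical hypothesis testing will be performed. An estimation approach will be used to assess the safety and immunogenicity objectives". SAP 5.1.2 adds: "Statistical decision rules will not be utilized in this study. All analyses are considered descriptive in nature".

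For the cellular assays, SAP 5.2.2.5 plans a "nonparametric comparison between each RSVpreF dose/formulation group and the placebo group on each of the assay values at each applicable time point", and "exact p-values based on the 2-sample Wilcoxon test will be provided for these comparisons". SAP 6.3.1 gives each group's median, n and range, and then says that "the exact p-value from the Wilcoxon 2-sample test will be used to compare each RSVpreF dose/formulation group and placebo group". SAP 6.3.2 (memory B cells and T cells) uses the same analysis.

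Neither section states a significance threshold, an adjustment, or an estimate of the difference between groups. The only sentence on multiplicity is in SAP 7.2, on the interim analyses: "No multiplicity adjustments will be applied for these analyses".

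The planned antibody comparisons between groups are handled differently. SAP 5.2.2.3, 6.2.1.2, 6.2.2.2 and 6.3.3 all give geometric mean ratios with 95% CIs.

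**The concern.** For the cellular endpoints the estimation approach stops at the single-group summaries. The comparison with placebo is a p-value alone. With about 10 subjects per group, a p-value says little about how large a difference is or how poorly it is estimated, and a reader needs both from an exploratory immunology readout.

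There is also a large set of comparisons against one placebo group. Stage 1 randomizes to "one of the 7 RSV vaccine doses/formulations or placebo (a total of 8 parallel groups), concomitantly with SIIV", so one unusual placebo group can produce several small p-values together.

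Two lesser points follow from the wording. If the prevaccination sample counts as an applicable time point, the plan tests randomized groups before Vaccination 1, which says nothing about the vaccine. And although a prevaccination cellular sample is drawn (Protocol 6.1.1) and baseline is defined (SAP 3.4.1), the comparison makes no use of it. The antibody assays, by contrast, get fold rises.

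**Working it through.** **The plan's own figures.** The documents give no alpha, power or error rate for these comparisons, so there is nothing to reproduce on this point. The sample-size table (Protocol Table 11) concerns adverse events. Its worked example checks: 1 − 0.95^31 = 0.796, stated as 80%.

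**Inputs from the documents**
- Stage 1: 7 vaccine arms and one placebo group (SAP 2.2).
- PBMC subset: about one third of subjects (Protocol 3.1). 250 / 3 / 8 = 10.4 per arm.
- Postvaccination times by endpoint (SAP 3.3): plasmablasts and T-cell phenotype at 1 week; memory B cells and T-cell frequencies at 1 and 6 months. Only a T-cell readout that falls in both lists has three times.
- Tests per readout: 7 × 1 = 7, 7 × 2 = 14, or 7 × 3 = 21.

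**Assumptions not in the documents:** no arm differs from placebo; p<0.05 two-sided is read as a signal; normal data without ties; within-subject correlation 0.5 between times.

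**Size of one test.** With 10 against 10, the exact two-sided Wilcoxon test at 0.05 has true size 0.0433. Expected false signals per readout are therefore 7 × 0.0433 = 0.30, 14 × 0.0433 = 0.61 and 21 × 0.0433 = 0.91.

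**Chance of at least one false signal per readout.** The independent-test value is 1 − (1 − 0.0433)^k. The other columns are simulated with the shared placebo group (40,000 null trials each).

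| Postvaccination times | Tests | Independent, n=10 | Shared placebo, n=10 | Shared placebo, n=11 |
|---|---|---|---|---|
| 1 | 7 | 27% | 20% | 22% |
| 2 | 14 | 46% | 36% | 37% |
| 3 | 21 | 61% | 46% | 49% |

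An 8,000-run simulation at n=10 gave 21.5%, 35.0% and 46.2%. As the correlation goes from 0 to 0.8 (n=10), the two-time figure moves from 37% to 31% and the three-time figure from 50% to 38%.

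**Use of baseline.** With equal variances and baseline correlation r, the variance relative to the raw value is 2(1 − r) for a change score and 1 − r² after linear adjustment. The documents give no r. Simulated power for a true shift of 1 SD (assumed), 10 per arm:

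| r | 2(1 − r) | 1 − r² | Raw Wilcoxon | Change-score Wilcoxon | ANCOVA |
|---|---|---|---|---|---|
| 0.2 | 1.60 | 0.96 | 0.50 | 0.34 | 0.55 |
| 0.5 | 1.00 | 0.75 | 0.53 | 0.52 | 0.67 |
| 0.8 | 0.40 | 0.36 | 0.52 | 0.88 | 0.92 |

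A change score breaks even at r of about 0.5 and loses below it. Under no effect, all three methods had simulated size of 0.04 to 0.05.

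**The case against.** The best defence is that the SAP already disclaims what the p-values might be taken to mean. It excludes only formal testing, sets no decision rule and calls everything descriptive, so the p-values are nominal by context. Medians and ranges by group also let a reader see roughly how far apart the groups are. This stands in part: it makes the point a minor one. It does not supply the missing difference and interval, which the antibody comparisons do receive.

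Four stronger readings are tempting, and the documents do not carry them.

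- *A false signal somewhere in the cellular results is more likely than not.* Pooling six endpoint-by-time combinations gives 7 × 6 = 42 tests, and simulation then gives 75% down to 51% for correlations of 0 to 0.8. But the cellular assay table in SAP 5.3.2 is blacked out, and SAP 3.3.5 commits only to CD4 and CD8 T cells, so the total cannot be verified. The pooled figure also needs all seven arms to be null: with three null arms at correlation 0.5 it is 42%.
- *Noise could be read as a CpG effect.* The cellular tests are against placebo only; no CpG versus Al(OH)₃ cellular test is planned. The adjuvant comparison in SAP 6.2.1.2 uses neutralizing titers, with ratios and CIs.
- *Dose selection will turn on these p-values.* SAP 7.2 says that the interim results overall inform selection. Nothing visible ties selection to a cellular p-value.
- *Leaving out baseline creates false signals.* In a randomized comparison it does not; it may cost precision.

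**Conclusion.** The point holds as a minor inconsistency in exploratory reporting. The cellular comparison with placebo does not deliver the estimation approach of SAP 5.1.1, because it yields p-values without a difference or an interval.

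Per Stage 1 readout, the chance of at least one false signal is about 20 to 22%, 35 to 37% or 46 to 49% for one, two or three postvaccination times. These figures depend on a 0.05 reading threshold that the SAP does not set, no true differences, 10 or 11 PBMC subjects per arm and a correlation of 0.5. The absence of adjustment is inferred from silence in SAP 5.2.2.5 and 6.3, since the explicit sentence belongs to the interim section. No primary or secondary endpoint is affected.

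**What to change.** In SAP 5.2.2.5 and 6.3.1 (6.3.2 follows by reference):

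1. For each vaccine group against placebo, report the Hodges-Lehmann difference with its exact 95% CI at each postvaccination time.
2. Drop the p-values, or label them nominal and unadjusted.
3. Make no between-group test at the time point before Vaccination 1. Prevaccination values can still be summarized by group.
4. If the prevaccination value is to be used, add a supportive baseline-adjusted analysis, such as rank or log-scale ANCOVA. Do not let a simple change score replace the raw comparison, because it loses precision when the baseline correlation is below about 0.5.

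The intervals would be unadjusted too, so this does not remove multiplicity. It shows the size and imprecision of each difference. The cost is a few lines of SAP text and some extra output; no new data are needed. Subjects without a prevaccination sample would drop out of the supportive analysis only.

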5.3. Methods to Manage Missing Data

5.3.1. Safety Data

Standard algorithms on handling missing AE dates and missing AE severity will be applied as described in the safety rulebook summary.

Missing data handling rules on the safety data are described in details the corresponding endpoint sections.

5.3.2. Immunogenicity Data

Any assay results above LLOQ are considered accurate and their quantitated values will be reported. Assay results noted as the upper limit of quantitation (ULOQ) will be set to the value of ULOQ for analysis. Values below the LLOQ or denoted as BLQ, or limit of detection (LOD), will be set to $0.5 \times \text{LLOQ}$ for analysis. For calculating a fold rise, $< \text{LLOQ}$ will be converted to $0.5 \times \text{LLOQ}$ for a numerator, and $< \text{LLOQ}$ will be converted to LLOQ for a denominator when only one of either the numerator or denominator is $< \text{LLOQ}$. If both the numerator and denominator are $< \text{LLOQ}$, then both will be converted in the same way.

CCI

CCI

CCI

PFIZER CONFIDENTIAL

Page 29

CCI

CCI

Values for sera that are insufficient (QNS), indeterminate results, or values recorded as “not done” will be set to “missing.” Additionally, any time point with no blood draws will not be included in the analysis. No imputation will be done for these missing values.

CCI

6. ANALYSES AND SUMMARIES

This section describes the analyses and summaries across all endpoints. In order to reconcile the protocol-specified endpoints (or estimands) and SAP template structure, the primary endpoints and secondary endpoints specified in the protocol are carried out in the “primary analysis” described in this section.

All exploratory endpoints specified in the protocol and the additional analyses for the protocol-specified primary and secondary endpoints are included in the “additional analysis,” “additional summary,” or “exploratory endpoints” sections in this document.

6.1. Primary Endpoints

6.1.1. Local Reactions

6.1.1.1. Primary Analysis

Endpoint: Proportions of subjects reporting prompted local reactions (pain at the injection site, redness, and swelling) within 14 days after vaccination.

- Analysis time points: Within 14 days after Vaccination 1.
- Analysis population: Safety population (Primary Study Cohort - Stage 1).
- Analysis methodology: Descriptive summary statistics.
- Supporting objective: Primary objective.

Reporting Results:

Proportions of subjects reporting prompted local reactions (each and any) after Vaccination 1 will be summarized by maximum severity level. Confirmed e-diary errors will be excluded from the analysis. The percentage (%), the numerator (n) and denominator (N) used in the percentage calculation, and the corresponding 95% Clopper-Pearson CI will be presented for each vaccine group.

6.1.1.2. Additional Summary for Assessing Local Reactions

To support the assessment of local reactions, similar endpoints will be summarized for the Primary Study Cohort - Stage 2 within 14 days after Vaccination 2; as well as for the RSV Vaccine Month-0, Month-2 Cohort within 14 days after Vaccination 1 and within 14 days after Vaccination 2.

To support the assessment of local reactions, additional endpoints (as defined in [Section 3.1.1](#)) will be summarized with all analysis time points (within 14 days after Vaccination 1 and within 14 days after Vaccination 2), analysis populations (Primary Study Cohort - Stage 1, Primary Study Cohort - Stage 2, and RSV Vaccine Month-0, Month-2 Cohort), analysis methodology, and appropriate reporting results. Confirmed e-diary errors will be excluded from these analyses.

CCI

PFIZER CONFIDENTIAL

Binary Endpoints

The percentage (%), the numerator (n) and denominator (N) used in the percentage calculation, and the corresponding 95% Clopper-Pearson CI will be presented for each vaccine group after each vaccination for the following endpoints:

- Subjects reporting any severe local reaction on each day and any day (Day 1 through Day 14).

Continuous Endpoints

The following endpoints will be summarized by displaying n, mean, median, standard deviation, minimum, and maximum for each vaccine group:

- Duration of each local reaction after vaccination.
- Onset day of each local reaction after vaccination.
- Onset day of any local reaction after vaccination.

Figures: Bar charts with the proportions of subjects reporting each local reaction within 14 days after vaccination will be plotted for each vaccine group. The bars will be stacked by maximum severity to highlight the proportions of subjects by severity.

6.1.2. Systemic Events

6.1.2.1. Primary Analysis

Endpoint: Proportions of subjects reporting prompted systemic events (fever, fatigue, headache, vomiting, nausea, diarrhea, muscle pain, and joint pain) within 14 days after vaccination.

- Analysis time points: Within 14 days after Vaccination 1.
- Analysis population: Safety population (Primary Study Cohort - Stage 1).
- Analysis methodology: Descriptive summary statistics.
- Supporting objective: Primary objective.

Reporting Results:

Proportions of subjects reporting prompted systemic events (each and any) after Vaccination 1 will be summarized by maximum severity level. Confirmed e-diary errors will be excluded from the analysis. The percentage (%), the numerator (n) and denominator (N) used in the percentage calculation, and the corresponding 95% Clopper-Pearson CI will be presented for each vaccine group.

6.1.2.2. Additional Summary for Assessing Systemic Events

To support the assessment of systemic events, similar endpoints as above will be summarized for the Primary Study Cohort - Stage 2 within 14 days after Vaccination 2; as well as for the RSV Vaccine Month-0, Month-2 Cohort within 14 days after Vaccination 1 and within 14 days after Vaccination 2.

To support the assessment of systemic events, additional endpoints (as defined in [Section 3.1.2](#)) will be summarized with all analysis time points (within 14 days after Vaccination 1 and within 14 days after Vaccination 2), analysis populations (Primary Study Cohort - Stage 1, Primary Study Cohort - Stage 2, and RSV Vaccine Month-0, Month-2 Cohort), analysis methodology, and appropriate reporting results. Confirmed e-diary errors will be excluded from these analyses.

Binary Endpoints

The percentage (%), the numerator (n) and denominator (N) used in the percentage calculation, and the corresponding 95% Clopper-Pearson CI will be presented for each vaccine group after each vaccination for the following endpoints:

- Subjects reporting any severe systemic events on each day and any day (Day 1 through Day 14).

Continuous Endpoints

The following endpoints will be summarized by displaying n, mean, median, standard deviation, minimum, and maximum for each vaccine group:

- Duration of each systemic event after vaccination.
- Onset day of each systemic event after vaccination.
- Onset day of any systemic event after vaccination.

Figures: Bar charts with the proportions of subjects reporting each systemic event within 14 days after vaccination will be plotted for each vaccine group. The bars will be stacked by maximum severity to highlight the proportions of subjects by severity.

6.1.3. Use of Antipyretic/Pain Medication

Use of antipyretic/pain medication will be analyzed in a similar way as systemic events ([Section 6.1.2](#)).

6.1.4. AEs

6.1.4.1. Primary Analysis

Endpoint: Proportions of subjects reporting AEs.

- Analysis time points: Within 1 month after Vaccination 1.
- Analysis population: Safety population (Primary Study Cohort - Stage 1).
- Analysis methodology: Descriptive summary statistics.
- Supporting objective: Primary safety objective.

Reporting Results:

The percentage (%), the number of subjects, the denominator (N) used in the percentage calculation, and the corresponding 95% Clopper-Pearson CI for subjects reporting any AE, each SOC, and each PT within SOC will be presented for each vaccine group.

6.1.4.2. Additional Summary for Assessing Adverse Events

To support the assessment of AEs, similar endpoints as above will be summarized for the Primary Study Cohort - Stage 2 within 1 month after Vaccination 2; as well as for the RSV Vaccine Month-0, Month-2 Cohort within 1 month after each vaccination and from Vaccination 1 through 1 month after Vaccination 2.

To support the assessment of AEs, additional endpoints by category (related AE, severe AE, SAE, MAE, immediate AE, AE leading to withdrawal, AE of specific interest), as defined in [Section 3.1.4](#), will be summarized with all analysis time points (within 1 month after Vaccination 1 and within 1 month after Vaccination 2), analysis populations (Primary Study Cohort - Stage 1, Primary Study Cohort - Stage 2, and RSV Vaccine Month-0, Month-2 Cohort), analysis methodology, and appropriate reporting results.

For each specific AE category (related AE, severe AE, SAE, MAE, immediate AE, AE leading to withdrawal), if the total number of subjects is >10% of the study population, the analysis summary by SOC and PT will also be provided for that category. Otherwise, only listings of these AEs will be provided by SOC, PT, and category designation (SAE, MAE, immediate AE, etc.).

If any nonserious AEs are reported to occur before vaccination or more than 1 month after vaccination (outside of the protocol-specified reporting window), they will not be summarized, but will be included in the AE listings.

Figures: Bar charts with the proportions of subjects reporting each AE category after vaccination will be plotted for each vaccine group.

